#### 9.6.5. Safety Analysis

#### 9.6.5.1. Analysis of the Primary Safety Endpoints

The primary endpoint is the incidence and severity of the following selected AEs reported post ide-cel infusion. These AEs are equivalent to the AESIs:

- All secondary malignancies
- CRS Grade  $\geq 3$

- Neurotoxicity Grade  $\geq 3$
- Prolonged cytopenias
- Pregnancy outcome
- Other AEs considered related to ide-cel treatment, for example:
  - o hypogammaglobulinemia
  - $\circ$  tumor lysis syndrome (TLS) Grade  $\geq$  3
  - serious infections (ie, requiring treatment)
  - $\circ$  organ toxicities Grade  $\geq 3$
  - others (eg, aggravated GVHD)

The primary endpoints will be analyzed and reported as described in Section 9.6.5.2 (below). Furthermore, suitable measures (incidence proportions and incidence rates) will be calculated with the appropriate time periods and methods. Analyses will be carried out without accounting for competing risks as well as accounting for competing risks using the cumulative incidence function method. Details are described in the SAP.

#### 9.6.5.2. General Handling and Analysis of Symptoms or Adverse Events

The registry collection of safety data is specific to certain symptoms of toxicity associated with CAR T cell therapy and recorded as safety outcomes. These safety data include CRS, neurotoxicity, hypogammaglobulinemia, TLS, infections, prolonged cytopenias, organ toxicities and secondary malignancies. All of the above, except for the secondary malignancies, are collected in a calendar format in an aggregate and summarized form based on the prior reporting period. Secondary malignancies, pregnancies and any deaths are reported on an event driven form upon knowledge at the site of care (center).

The incidence of organ toxicities will be summarized by Medical Dictionary for Regulatory Activities (MedDRA) system organ class (SOC) and preferred term (PT). Organ toxicities will be graded using National Cancer Institute Common Terminology Criteria for Adverse Events (NCI CTCAE) Version 5.0 or higher. Only organ toxicities of Grade 3 (severe), Grade 4 (life-threatening), and Grade 5 (death) will be summarized in reports. A patient who reports multiple occurrences of an organ toxicity with the same SOC and PT is counted only once using the maximum severity grade for summaries. If a patient experiences the same organ toxicity more than once with different grades, then the event with the highest grade will be tabulated in "by grade" tables. If a patient experiences multiple organ toxicity under the same PT and SOC, then the patient will be counted only once for that PT (SOC).

The incidence of each AESI and of most frequent AEs ( $\geq 10\%$ ) will be summarized using the number and percentage of patients experiencing the event. Exact 95% Clopper Pearson CIs will be provided for the percentages.

Adverse Events will be reported according to the following structure:

1) **Overall Summary of Organ Toxicities/Symptoms:** Summaries of AEs will be produced overall as described above.

- 2) Summaries by System Organ Class and Preferred Term: Summary tables by SOC and PT of the number of events and the number, percentage and exact 95% Clopper Pearson CIs for patients having events will be presented separately for each of the event types.
- 3) **Summaries by System Organ Class, Preferred Term and Highest Grade:** Events will be presented by SOC, PT and highest grade. Number, percentage and exact 95% Clopper Pearson CIs of patients for each of the event types will be presented using the patient's maximum grade.

Other toxicological symptoms recorded using free text fields are coded using SOC and PT based on the most recent version of the MedDRA.

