#### 9.3. Variables

The following variables will be recorded and used within this study:

Classification	Category	Variable	Description
		Patient Code / ID	Unique de-identified ID for patient
		Reporting Center (RC) Name / ID	Center name or ID reporting to the registry
Baseline (at infusion date)	General Identifiers	Manufacturing Site (MFS) Name /ID	Site name or ID producing the CAR T product
(at infusion date)		Apheresis Center (AC) Name / ID	Center name or ID conducting leukapheresis
		Site of Care (SC) Name / ID	Center name or ID treating patient and infusing the CAR T product
		Product Name	Name of CAR T product
Baseline	Product Information	Product Code / ID (Join ID)	Product ID for the first product
		Product Quality: OOS	Product: out of specification, yes/no
	Key Treatment Processes and Timing	Patient Registering Date	Date patient was registered into the registry DB by the RC
		Leukapheresis Date	Date blood was collected at the AC
		Blood Shipment Date	Date blood was shipped from the AC to the MFS
		Blood Arrival Date	Date blood arrived at the MFS
		Manufacturing Start Date	Date MFS started production of CAR T
		Manufacturing End Date	Date MFS completed production of CAR T
		Product Shipment Date	Date CAR T was shipped to the SC
Baseline		Product Receipt Date	Date CAR T arrived at the SC
		Lymphodepleting Therapy Date	Date when lymphodepleting therapy started at SC
		Infusion Date	Date when CAR T was infused to the patient at the SC
		Product Infusion Count	Infusion counting number and total number of infusions
		Diagnosis Date	Date when primary disease was diagnosed
		Last Contact Date	Date when patient was last time in contact with the SC
		Safety Assessment Date	Date of any safety assessments findings (as listed in the safety section below)
		Effectiveness Assessment Date	Date of any effectiveness assessments findings (as listed in the effectiveness section below)

Confidential and Proprietary

Table 4: Variables (Con	tinued)
-------------------------	---------

Classification Category		Variable	Description
		Age	Age at infusion (years)
		Weight	Body weight at infusion (kg)
Deseline	Democratica	Height	Body height at infusion (cm)
Baseline	Demographics	Gender	Gender of patient
		Country	Country of the infusion center
		Region	Region of treatment: North America/Europe/Japan/Rest of the World
		Karnofsky Performance Score	Karnofsky performance score at infusion

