	Clinical Variables (Disease History/ Prior Therapy/ Infusion Related)	ECOG Performance Score	ECOG performance score at infusion
		Disease History/Co-Morbidity	Comorbidity prior to infusion and organ involvement (eg, cardiac, hepatic, obesity, pulmonary renal, diabetes, solid tumor, and others)
		Prior Therapy 1: Lines	Number of prior therapy lines
		Prior Therapy 2: List	Names of prior therapies (systemic therapies, standard regimens)
		Prior Therapy 3: HCT	Number of prior hematopoietic cell transplantations (HCTs)
Baseline		Prior Therapy 4: HCT Type	Types of prior HCTs
		Disease Status 1: Primary Disease	Primary disease and disease status prior to LD chemotherapy
		Disease Status 2: International Staging System	Classification according to albumin and beta 2 microglobulin levels into stages I, II or III
		Disease Status 3: Cytogen. FISH	Chromosome changes identified via FISH at diagnosis
		Disease Status 4: Cytogen. Karyotyping	Chromosome changes identified via karyotyping at diagnosis
		Lymphodepleting Treatment	Types and names of lymphodepleting chemotherapy agents

Classification	Category	Variable	Description
		Secondary Malignancies (SM)	Subsequent neoplasms assessment and types of SM reported during FU
		Cytokine Release Syndrome 1: Presence	Assessment and presence of CRS reported during FU
		Cytokine Release Syndrome 2: Grade	CRS grade
		Cytokine Release Syndrome 3: Symptoms	CRS symptoms: fever, hypotension, hypoxia
		Cytokine Release Syndrome 4: Therapy	CRS therapy: intraven. fluids, vasopressors, positive pressure vent support, other therapy, CRS resolution date
		Neurotoxicity 1: Presence	Assessment and presence of NT reported during FU
		Neurotoxicity 2: Grade	NT grade
Outcome (reported at 100 d,	Safety	Neurotoxicity 3: Symptoms	NT symptoms: consciousness, dysphasia, seizure, paraparesis, cerebral edema, hallucination, tremors, other neurologic symptoms
		Neurotoxicity 4: Therapy	NT therapy: antiepileptic and other therapy given, NT resolution date
		Prolonged Cytopenia 1: Presence	Neutrophil count $< 500/\text{mm}^3$ , platelet count $< 20 \text{ x } 10^9/\text{L}$
		Prolonged Cytopenia 2: Recovery	Neutrophil and platelet recovery
6 months, yearly)		Hypogammaglobulinemia 1: Presence	Assessment and presence of hypogammaglobulinemia during FU
		Hypogammaglobulinemia 2: Therapy	Hypogammaglobulinemia therapy (immunoglobulin replacement) and resolution
		Tumor Lysis Syndrome 1: Presence	Assessment and presence of TLS reported during FU

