#### Table 4:Variables (Continued)

Confidential and Proprietary

Classification	Category	Variable	Description
	Effectiveness	Best Overall Response 1: Biochemical Assessment	Assessment of response based on biochemical assessment
		Best Overall Response 2: Bone Marrow Assessment	Assessment of response based on bone marrow assessment
		Relapse and Progression 1	Outcome of relapse or progression detected by bone marrow and/or biochemical/radiologic assessment
Outcome		Relapse and Progression 2: Therapy	Therapy given for treatment of relapse or progression
		Progression Status	Status of progression
		Relapse Status	Status of relapse
		Cause of Death	Primary cause of death and contributing causes of death #1 to #4
		Survival Status	Survival status at last contact

AC = apheresis center, AE = adverse event, ASTCT = American Society for Transplantation and Cellular Therapy, B2M = beta 2 microglobulin, CAR T = chimeric antigen receptor T cell, CRS = cytokine release syndrome, CT = cell therapy, Cytogen. = cytogenetic, d = day, DB = database, ECOG = Eastern Cooperative Oncology Group, FISH = fluorescence in situ hybridization, FU = follow-up, GVHD = graft-versus-host disease, HCT = hematopoietic cell transplantations, ID = Identifier, Intraven. = intravenous, LD = lymphodepleting, MFS = manufacturing site, NT = neurotoxicity, OOS = out of specification, RC = reporting center, SC = site of care, SM = secondary malignancies, TLS = tumor lysis syndrome.

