#### 9.6.4. Effectiveness Analysis

#### 9.6.4.1. Analysis of the Secondary Effectiveness Endpoints

- **Overall Survival (OS)**: Overall survival is defined as the time from the date of first infusion to the date of death due to any cause. All patients will be followed for survival information, regardless of whether they receive additional treatment post-infusion. Patients who are alive at last contact date will be censored at that time, but no censoring will be done for additional treatment.
- **Progression-Free Survival (PFS)**: PFS is defined as the time from the date of first idecel infusion to the date of event defined as the first documented relapse or progression or death due to any cause, whatever happens first. Patients who are alive at last contact date will be censored at that time, but no censoring will be done for additional treatment.
- **Time To Event (TTE) Analysis:** Kaplan-Meier estimates and the associated 95% CIs of the median, 25th and 75th percentile will be presented. The two-sided 95% CIs will be computed using the log-log transformation. The survivor function will be displayed graphically using a KM curve.

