## 9.8. Limitations of the Research Methods

As this is an observational PASS based upon secondary use of data, sporadic missing data are inevitable, because certain variables may not have been routinely recorded in the patient medical charts. Furthermore, data will also be missing due to gaps in the follow-up (as routine scheduled visits cannot be mandated in an observational study), and loss to follow-up, especially in this study with a planned duration of 15 years. Details of how missing data are handled are also outlined in the SAP.

The above-mentioned potential issue can lead to significant biasing effects on time to event analyses as well as analyses quantifying a duration. In the EBMT and the CIBMTR registries, data are recorded at baseline, 100 days, 6 months and then yearly. Thus, owing to center specific different levels of compliance, a high variability in the recording of assessment dates is to be expected.

To minimize selection bias, sites are requested to ask every patient treated with ide-cel to share data with the registry. Nevertheless, not all patients will consent to have their data sent to the

Confidential and Proprietary

EBMT or the CIBMTR registries, possibly resulting in a biased sample of patients. A high rate of attrition (particularly if mortality is not captured well) could bias the results. In addition, in order to monitor the reporting, the study team will reconcile shipped products to each center participating in the study with the subsequent compliance of the patient and center with the study.

Additionally, as with every observational study, there will be unmeasured factors that can confound safety and effectiveness analyses. This PASS will attempt to collect accurate and complete data on all known critical confounders; however, residual confounding is always a possibility in any observational study analysis.

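### Deaths and secondary malignancies are reported as they occur but survivors are censored at last contact, so early Kaplan-Meier and person-time estimates are likely to run high

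*Protocol*

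**What the plan says.** The protocol sets up two reporting streams. Section 9.6.5.2 collects most toxicities in calendar format for the preceding reporting period, but "Secondary malignancies, pregnancies and any deaths are reported on an event driven form upon knowledge at the site of care (center". Section 9.8 gives the routine schedule: "In the EBMT and the CIBMTR registries, data are recorded at baseline, 100 days, 6 months and then yearly".

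Table 4 (section 9.3) defines the last contact date as "Date when patient was last time in contact with the SC" and records "Survival status at last contact". It also puts secondary malignancies ("Subsequent neoplasms assessment and types of SM reported during FU") in the outcome block reported at 100 days, 6 months and yearly, which does not match the event-driven form of section 9.6.5.2.

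Section 9.6.4.1 fixes the censoring rule for OS and PFS: "Patients who are alive at last contact date will be censored at that time, but no censoring will be done for additional treatment". Section 9.6.5.1 adds, for the primary safety endpoints, that "suitable measures (incidence proportions and incidence rates) will be calculated with the appropriate time periods and methods", together with cumulative incidence functions, and leaves details to the SAP. Interim reports fall at years 5, 10 and 15 after the EC decision, and safety reports every 6 months (section 6, Table 2).

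**The concern.** How far a patient's record reaches can depend on the outcome. A death becomes known when the centre hears of it. Survival is confirmed only up to the last contact on file.

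Take two patients infused 1.9 years before a data cut, and suppose contact dates come from scheduled forms. The one who died last week contributes a death at about 1.9 years. The one still alive is censored at 1.0 year. Time after the last form therefore enters only for patients with an event, and censoring is informative.

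The result is overstated mortality, shortened OS and an overstated secondary malignancy rate, which is one of the primary endpoints. The bias resembles a safety signal. It is largest when much of the follow-up is recent, and the year-5 interim falls near the end of a selection period of up to 5 years.

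**Working it through.** **The protocol's own figures.** It gives none for this bias. The nearest are the Table 5 Clopper-Pearson intervals for 1000 patients, and they reproduce: 35/1000 gives 0.0245 to 0.0483 (stated 0.025 to 0.048), 43/1000 gives 0.031 to 0.058, 61/1000 gives 0.047 to 0.078, and 30/1000 gives 0.020 to 0.043. These are proportions with no person-time denominator, so the mechanism does not inflate them.

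**Inputs from the protocol.** 1000 patients over up to 5 years; forms at 100 days, 6 months, then yearly; survivors censored at last contact; deaths and malignancies reported when known.

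**Assumptions not in the protocol.** Uniform accrual over 5 years; exponential OS (no OS figure is given, so a range of medians is used); malignancy rate 0.01 or 0.02 per person-year; last contact moves only with scheduled forms; reporting delays as stated below.

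**Closed-form check, year-5 cut, no delays, median OS 30 months.**
- Hazard λ = ln 2 / 2.5 = 0.2773 per year.
- Proportion alive at the cut: p = (1 − e^(−5λ)) / (5λ) = 0.750 / 1.387 = 0.541.
- Mean time to death or cut: m = (1 − p) / λ = 0.459 / 0.2773 = 1.655 years.
- Mean unconfirmed time per survivor, from simulation: g = 4.58 months = 0.382 years.
- Estimated over true rate: m / (m − p·g) = 1.655 / (1.655 − 0.207) = 1.14.

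The full simulation also gives 1.14 for mortality. The malignancy rate loses the same kind of person-time and comes out at 1.12.

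**Simulation by data cut** (300,000 patients per scenario, no delays, median OS 12 to 48 months):

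| Cut | Mortality rate overstated by |
|---|---|
| Year 2 | 27–42% |
| Year 3 | 17–30% |
| Year 5 | 9–16% |
| Year 10 | 0.2–4% |
| Year 15 | below 1% |

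At year 5 the Kaplan-Meier median reads 18.3 months for a true 20, 26.7 for 30 and 40.1 for 48. With a true median of 30 months, 3-year survival of 0.436 reads 0.389.

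**Sensitivity to delays, year-5 cut** (median OS 1.5 to 3 years):

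| Delay | Rate overstated by |
|---|---|
| None, or 3 months on both forms and event reports | about 9–15% |
| 3 months on event reports only | about 4–7% |
| 3 months on forms only | about 18–24% |

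A true median OS of 2.0 years reads about 1.8 with no delay and about 1.7 if only forms are late. With a mean 3-month delay in death reports only, true medians of 20 and 30 months read 19.2 and 28.4. The bias shrinks but does not reverse.

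**After matching the windows.** When events and time both end at the last scheduled form due, the mortality rate ratio is 0.99 to 1.01 in every scenario, and year-5 Kaplan-Meier survival for a 30-month median returns to the true 0.758, 0.574 and 0.436 at 1, 2 and 3 years.

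**The case against.** **The SAP may settle it.** Section 9.6.5.1 leaves time periods and methods for the safety rates to the SAP, and section 9.8 does the same for missing data. This stands: the lack of a person-time rule for malignancy in the protocol is not itself a defect. It does not cover the OS and PFS censoring sentence, which section 9.6.4.1 already fixes without a matching limit on events. Censoring at last contact is common wording and is compatible with a cut-off rule, but the rule has to be added.

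**Last contact may move between forms.** A reader might infer that the protocol ties last contact to the scheduled form. It does not: Table 4 defines it as actual contact with the site of care. The protocol describes no other route by which the date is refreshed, but more frequent updating would shrink the bias.

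**Event reports can also be late.** They are filed only once the centre knows, and section 9.8 warns that mortality may be poorly captured, which acts in the opposite direction. Hence the lower 4–7% figure. The largest figures need late forms with immediate event reports and should not be taken as the central estimate.

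**Section 9.8 already warns of bias.** It does so in general terms, citing follow-up gaps and variable assessment dates. It does not mention event-driven against scheduled reporting, and it supplies no correction.

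**Conclusion.** The concern holds for time-based estimates made during or soon after accrual. At the year-5 interim the likely overstatement is about 9–15%, with a plausible span from about 4% (only event reports late) to about 25% (only forms late). These sizes rest on exponential OS, uniform 5-year accrual and contact dates driven by scheduled forms. Faster accrual or more frequent contact updates would reduce them.

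Three stronger readings are not supported:
- That every interim report is materially biased. The error is about 1–4% at year 10 and negligible at year 15.
- That the primary safety results as a whole are inflated. The numbers and percentages with Clopper-Pearson intervals in section 9.6.5.2 are not. For PFS, only the death component is affected by event-driven reporting.
- That the 6-monthly safety reports carry the bias. The protocol does not say they contain Kaplan-Meier or person-time estimates; if they do, the year-2 and year-3 figures above show the possible size.

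This should be corrected before the first time-to-event analysis.

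**What to change.** State in section 9.6.4.1, and carry into the SAP for the section 9.6.5.1 rates and cumulative incidence, that events and follow-up time share one window per patient. The window ends at the last scheduled follow-up form due before the data cut, with an allowance for form completion, or at the last completed form for patients out of contact. Event-driven reports dated after that point are listed separately and enter at the next cut.

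Reconcile Table 4 with section 9.6.5.2 on whether secondary malignancies are reported on schedule or event-driven.

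A single global cut-off set 12 + 3 months before extraction is not an equivalent rule and should not be used. It would drop about 35–38% of events at year 5 and about 60% at year 3.

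The cost is a wording change and one derived date per patient. About 11–14% of events known at the year-5 cut (18–21% if forms run 3 months late) move from the rate analysis to a listing until the next report. No safety information is withheld.

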## 9.7. Quality Control

#### 9.7.1. Quality Control Performed by the EBMT and the CIBMTR Registries

The study will be conducted according to the guidelines for Good Pharmacoepidemiology Practice (GPP) (International Society for Pharmacoepidemiology 2015) and according to the ENCePP code of conduct (EMA, 2018).

Data in the PASS will be managed according to the processes of the EBMT and/or the CIBMTR. The quality control details will be further described in the operational plans of the EBMT and/or the CIBMTR which will be written for this study specifically.

The EBMT and/or the CIBMTR will secure the data in line with local applicable regulatory law and procedures. Access will be limited to authorized individuals only. Controls, such as document encryption, will be used to ensure the authenticity, integrity and confidentiality of electronic records when transmitted over open systems (eg, the internet). The study data are adequately backed up at regular intervals.

All individuals at sites responsible for the integrity of the data will be trained by the EBMT and/or the CIBMTR staff on the requirements of the PASS.

For data stored at the corresponding registries, the standard processes of the EBMT and/or the CIBMTR will be followed. This procedure will ensure the quality of the data in the registry and will ensure that the data are reviewed and queried on an ongoing basis to support data accuracy and completeness. In addition, the system will contain automatic edit checks that validate data entry according to prespecified standards, as well as regular data review by data management and site monitors that will generate manual edit checks to ensure the quality of data.

Furthermore, the data from the EBMT and/or the CIBMTR registries will be checked against source documents for 10% of patients; this approach will be risk-based and can be done remotely and/or on site. Details will be documented in the specific operational plans of both organizations.

#### 9.7.2. Quality Control Performed by the Sponsor

The Sponsor retains the right to audit the study data and processes of the EBMT and the CIBMTR at any time if required. Findings of such audits will be documented and filed. If necessary, appropriate measures will be taken if issues are detected at audits.

The Sponsor will develop and implement an internal platform to store all data obtained in the frame of this study from external sources. These data will be assumed clean and no quality control procedures will be applied to the raw data because the quality of these data, and the source verification is the responsibility of the registry holders as described in Section 9.7.1 and Section 9.7.3.

Any data manipulation (eg, merging, transformation, calculations) will be documented according to appropriate data management practices used by the Sponsor for clinical trial data (eg, programming data specifications, data management plan) using appropriate quality control measures.

